Photograph Review. The Sponsor will train an independent reviewer to read DilaCheck® measurements. The reviewer will be provided the photographs taken of DilaCheck® measurements. The reviewer will report two measurements for each photograph. The first will be his/her reading of the exact DilaCheck® measurement, which may be a fraction. The second reading will be his/her reading of the DilaCheck® measurement rounded to the nearest integer; i.e. the second response can only be an integer, not a fraction.

Continuous Feedback. After any individual provider completes five examinations with DilaCheck®, the provider will be provided feedback about whether his/her DilaCheck® measurement readings match those of the independent reviewer.

Power Calculation. The planned enrollment in the study is 50 patients. The following assumptions were used for the power calculations. The agreement in the Control Group was projected to be 49%,⁴ and the agreement in the Device Group was projected to be 90%, based on the results of the simulator trial. The standard deviation was projected to be 23, also based on the standard deviation in the prior simulator trial. With a two-tailed test with $\alpha=0.05$, a sample size of five yields 80% power. However, a trial with five participants will not yield the desired robustness in evaluation of a novel medical device. Instead, a sample size of 25 subjects in each group is planned to allow for examinations across a wide range of patients and providers. A sample size of 50 yields a power of 100% to detect a difference between the two methods given the above assumptions.

Statistical Analysis. The statistical analysis will use a two-tailed level of significance of 0.05. Using SPSS, the proportion of examinations in each group for which the two providers' examinations differed will be determined. A Students T test will be performed to determine whether this difference is significant. The number of examinations for which providers' answers differed by one centimeter and by two or more centimeters for each group will be determined. A Students T test will be performed to determine if the frequency of variation of one centimeter significantly differed between groups. A Students T test will be performed to determine if the frequency of variation of two or more centimeters significantly differed between groups. These analyses will be completed for both the fractional and integral (non-fractional) sets of DilaCheck® measurement readings.

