For participants in the DilaCheck® arm, the subjective and DilaCheck®

DilaCheck® Trial

measurements will be plotted along an X-Y axis and the Pearson correlation coefficient between the two data sets will be calculated. This analysis will be completed for both the fractional and integral (non-fractional) sets of DilaCheck® measurement readings.

The photographs of the DilaCheck® measurements will be read by an independent, blinded reviewer to report the DilaCheck® measurements. The provider's and reviewer's DilaCheck® measurements will be plotted along an X-Y axis and the Pearson correlation coefficient between the two data sets will be calculated. This analysis will be completed for the fractional and integral (non-fractional) sets of DilaCheck® measurement readings.

The correlation between the providers' subjective and DilaCheck® measurements will be analyzed over time. To do so, for providers who complete at least 10 exams, the correlation of the two measurements in the provider's first half of examinations will be compared to the providers' second half of measurements. A T-test will be completed to determine whether the two correlations differ significantly. The analysis will be repeated for both the fractional and integral (non-fractional) sets of DilaCheck® measurement readings and using the data sets of readings from the independent reviewer.

The average pain score in each group will be calculated, and a Students T test will be performed to determine whether pain scores differed significantly between groups. Using logistic regression whether provider number, patient age, gestational age, weight, or epidural status significantly impacted likelihood of agreement or pain score within each group will be determined. The average provider confidence in accuracy will be calculated, and a Students T test will compare if patients' confidence differs significantly between groups. Logistic regression will be used to determine if provider experience or training significantly predicted likelihood of agreement.

Any additional statistical analysis appropriate for the data collected will be performed. For the qualitative data, including descriptions of adverse events and feedback, each of the responses will be reviewed individually. Any serious adverse events will be reported. Any informative feedback or themes in the feedback will also be collated.

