With regard to missing data, if a patient is missing one or both of the cervical dilation readings, she will be excluded from analysis of the primary outcome. However, if she has filled out a survey, this data will be used in the analysis of secondary outcomes since it may include important data accounting for why the patient was unable to have both examinations. If a patient or provider is missing one or more answers to a survey question, then the response to that question will be omitted from the analysis. The statistical analysis will not include imputing missing data.

The Sponsor will provide the trial coordinator, principle investigator, and other

involved TJU staff access to the statistical analysis and article draft and provide them with time to provide feedback and insight into all statistical analyses.

Study Device Specifications. There are no hazardous materials involved in this trial. The study device is made of soft, medical grade, biocompatible components. The device is sterilized using gamma radiation. The device is not anticipated to present any risk above that of a standard cervical dilation examination with a sterile glove. It is tested for reliability, and all components have multiple attachment points so that if one attachment point fails, it will still be attached to another component or the provider's hand and thus will not be left in the patient.

Bias. Unfortunately, it is not feasible to blind patients and providers to group assignment. However, keeping the second provider blinded to the first provider's measurement will decrease bias. Randomization using a computer generation program will also eliminate assignment bias.

Potential Problems. Given the acuity of Labor and Delivery, one anticipated challenge is enrollment. Women in labor may be hesitant to participate in any clinical trial or to participate in the validation of a novel device. We will offer a small incentive for participation via a modest gift certificate of a size not large enough to coerce patients into participating. The trial coordinator will answer any questions the patient has regarding the trial and respond to any concerns that arise in an open, patient, and honest manner.

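### The device-arm agreement models would rest on about 2.5 disagreements, and the t-test named for three yes/no outcomes can exceed the stated 5% error rate by a modest amount

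*Combined protocol and SAP*

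**What the plan says.** The Statistical Analysis section of the combined protocol and SAP sets the error rate: "The statistical analysis will use a two-tailed level of significance of 0.05". It takes the proportion of examinations in each group in which the two providers differed and states "A Students T test will be performed to determine whether this difference is significant". It prescribes the same test for differences of one centimetre and again for larger ones: "A Students T test will be performed to determine if the frequency of variation of two or more centimeters significantly differed between groups".

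The same section then plans predictor models: "Using logistic regression whether provider number, patient age, gestational age, weight, or epidural status significantly impacted likelihood of agreement or pain score within each group". A further model follows: "Logistic regression will be used to determine if provider experience or training significantly predicted likelihood of agreement". The pain score is also compared between arms as a mean: "The average pain score in each group will be calculated, and a Students T test will be performed".

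The Power Calculation section plans 25 patients per group and projects 49% agreement in the control arm; for the device arm, "the agreement in the Device Group was projected to be 90" per cent. The missing-data paragraph says that "if a patient is missing one or both of the cervical dilation readings, she will be excluded from analysis of the primary outcome", so the analysed arms may be smaller than 25.

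**The concern.** A logistic model of agreement learns from the rarer outcome, here disagreement. If the device works as projected, disagreement almost vanishes in its arm, and five predictors are to be judged on a handful of events. The plan promises to say which predictors significantly affected agreement. With so few events, a null finding means little and a positive one may be an artefact of one or two patients.

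Each of the three between-arm outcomes is one yes or no per patient, whereas Student's t-test is built for means of continuous measurements. At stake is whether the stated two-sided 5% is the error rate that the trial would actually have.

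**Working it through.** **Inputs.** 25 per arm, 49% and 90% agreement (Power Calculation); two-sided 5% (Statistical Analysis). Patients are treated as independent; providers shared between patients are not modelled.

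**The plan's own figure.** With a difference of 41 points and SD 23, 2 × (23 × (1.960 + 0.842) / 41)² = 4.94, or five per arm. Power at 25 per arm is then 99.999%. The stated five and 100% therefore reproduce as a comparison of means. The power figures below are lower because they use the yes/no scale.

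**Within-arm agreement models.**
- Expected device-arm disagreements: 25 × 0.10 = 2.5. Control arm: 25 × 0.51 = 12.75, leaving 12.25 agreements.
- With Binomial(25, 0.10), P(none) = 0.9²⁵ = 7.2%, P(three or fewer) = 76.4% and P(four or fewer) = 90.2%.
- All five predictors together, one parameter each at the least: 2.5 / 5 = 0.5 events per parameter in the device arm, and 12.25 / 5 = 2.45 in the control arm.
- One standardised predictor alone, with no true effect: SE of the log odds ratio = 1/√(n p (1 − p)), and 95% CI = exp(±1.96 × SE). This is a large-sample formula, so at these counts it is only a guide.

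| Arm and agreement | Expected disagreements | SE | 95% CI for odds ratio per SD |
|---|---|---|---|
| Device, 80% | 5.0 | 0.500 | 0.38 to 2.7 |
| Device, 90% (projected) | 2.5 | 0.667 | 0.27 to 3.7 |
| Device, 95% | 1.25 | 0.918 | 0.17 to 6.0 |
| Control, 49% | 12.75 | 0.400 | 0.46 to 2.2 |

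- A yes/no predictor, assuming a 12/13 split: with three disagreements, the most extreme pattern has exact p = C(12,3)/C(25,3) = 220/2300 = 0.096. Three or fewer disagreements therefore cannot reach 0.05 at that split. A more uneven split can.

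**The t-test on 0/1 data.** With φ the correlation in the 2×2 table and N = 50, the uncorrected chi-square is X² = Nφ² and t² = (N − 2)φ²/(1 − φ²). The 5% critical t on 48 df is 2.011 (square 4.043), which corresponds to X² = 50 × 4.043/(4.043 + 48) = 3.884, against the usual 3.841. None of the 26 × 26 = 676 possible tables falls between the two, so the tests always agree.

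**Exact size.** This is the sum of the binomial probabilities of every rejecting table, with both arms at 49% agreement.

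| Analysed per arm | t-test size at 49% | Maximum over all common rates |
|---|---|---|
| 25/25 | 6.5% | 6.5% |
| 24/25 | 4.5% | 5.3% |
| 24/24 | 5.9% | 6.0% |
| 23/25 | 6.0% | 6.0% |

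At 25/25 and 49%, Boschloo's test has size 3.7% (maximum 4.6%) and Fisher's 3.3%. The t-test's size at 25/25 falls to 2.0% when the common rate is 5%, so it is not inflated for sparse outcomes.

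**Effect on the primary result.** The projections correspond to about 12/25 versus 22/25 agreeing. That gives p = 0.002 (t-test), 0.003 (Boschloo) and 0.005 (Fisher). At 49% versus 90%, the t-test and Boschloo's reach different decisions in 1.4% of trials.

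**The case against.** The t-test is prespecified and equivalent here to a conventional chi-square test, and its excess over 5% comes from the discreteness of the exact arm sizes. Losing a single patient brings it below 5% at the 49% rate. This stands, and it limits the t-test point to a modest one.

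Four stronger readings are tempting and are not supported.
- A reader might infer that the primary comparison is untrustworthy. The projected result is significant under every test considered.
- A reader might take a sparse result such as 4/25 versus 0/25 as evidence against the t-test, since it gives p = 0.038 and Fisher's gives 0.110. Barnard's, a valid exact test, gives 0.041, so the spread shows only that valid tests differ among themselves. The plan already fixes one test for that outcome.
- A reader might infer that provider number will be entered as a numeric predictor, or that all five predictors enter one joint model. The plan says neither.
- A reader might call logistic regression wrong for the pain score. An ordinal logistic model is a possible reading, so the gap is missing detail.

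On the within-arm models, one can object that they are secondary, that no decision is attached to them, and that 90% is only a projection from a simulator. Readings recorded to any fraction may also disagree more often than integer readings. All of that is fair, but at 80% agreement only 5.0 disagreements are expected. The allowance for additional appropriate analyses adds to the named models without replacing them.

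**Conclusion.** The concern holds in two parts of unequal weight. The more substantive is the device-arm agreement modelling. On the plan's own projection it would rest on about 2.5 events, and it cannot give reliable results in joint or single-predictor form at any agreement rate from 80% to 95%. It affects secondary findings only.

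The other part is the t-test for three yes/no outcomes. At exactly 25/25 and a 49% common rate it exceeds the stated 5% by about 1.5 points. With one or two exclusions the excess at that rate ranges from none to about one point. The primary conclusion is unlikely to change. These figures assume independent patients.

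Two matters need clarification only: the pain-score scale and model form, and how the values of two providers enter a single agreement outcome.

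**What to change.** - Replace the within-arm agreement models with descriptive summaries. Alternatively, fit one pooled, penalised model, labelled exploratory, with arm and one or two prespecified covariates; it would draw on 12.75 + 2.5 = 15.25 expected disagreements.
- Name one unconditional exact test for all three agreement outcomes. Boschloo's is one suitable choice. Report each difference in proportions with a Newcombe 95% CI; for 12/25 versus 22/25 that is 40 points (14.2 to 59.6).
- The plan names SPSS. If no unconditional test is available in the software used, write Fisher's into the plan before analysis, with no switch afterwards.
- State the pain-score scale and the form of its model, and say how two providers' numbers, experience or training enter one outcome.

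**Cost.** Wording only, with no new data. Exact power at 25 per arm is:

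| Agreement, control vs device | t-test | Boschloo | Fisher |
|---|---|---|---|
| 49% vs 90% | 92.3% | 90.9% | 85.1% |
| 49% vs 80% | 66.5% | 63.3% | 54.1% |

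Fisher's costs clearly more and should remain the fallback. Dropping the within-arm models loses nothing that they could reliably have shown in the device arm.

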Trial Coordination. After training, the Sponsor or the trial coordinator will orient the provider to the study protocol and assign every provider a unique Provider Number. The trial coordinator will arrange with the hospital staff to conduct the trial at scheduled times during the study period. Administration of the trial requires two hospital providers who have been trained to use the device, the trial coordinator,

and a patient.

Patient Enrollment. Hospital providers will screen patients who have been admitted to the Labor and Delivery unit for eligibility. Posters advertising the trial will also be displayed on the Labor and Delivery unit. Once identified, hospital providers will ask eligible patients if they are interested in participating. If a patient indicates interest, the trial coordinator will complete an informed consent. The patient will sign the Patient Informed Consent Form.

Randomization. The trial coordinator will assign the participant a Subject Number from one to 50, in sequential order. (The first patient enrolled is assigned #1, the second enrolled is assigned #2, and so on.) The trial coordinator will then randomize the patient to either the Control Group or the Device Group using a randomization matrix generated by a computer randomization program.

Data Collection. The trial coordinator will inform two trained providers that the patient has agreed to participate in the trial. The trial coordinator will accompany one hospital provider to the patient's hospital room. The second provider will wait outside the room, in a place where s/he cannot hear the interaction in the room. The trial coordinator will re-affirm consent with the patient.

If the patient is randomized to the Control Group: The first provider will introduce him/herself and inform the patient that s/he is going to conduct a cervical examination. The trial coordinator will record the time of the first exam. The provider will complete a cervical examination following the standard techniques s/he uses on a regular basis, using sterile gloves. The provider will dispose of the gloves. The first provider will write his/her measurement of cervical dilation on the first Data Collection Form and fold the sheet of paper. Readings may be integers or fractional answers. The coordinator will take the folded sheet of paper and will not read the value. The first provider will then leave the hospital room. S/he will not speak to the second provider.

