The second provider will enter the hospital room. The second provider will introduce him/herself to the patient and explain that s/he is going to perform a cervical examination. The trial coordinator will record the time of the second exam. The second exam must be completed within 10 minutes of the first exam. The second provider will complete a cervical examination following standard techniques. The provider will write his/her measurement of cervical dilation on a second Data Collection Form, fold the form, and hand it to the trial coordinator. Readings may be integers or fractional answers. The second provider will leave the room.

If the patient is in the Device Group: The first provider will introduce him/herself and inform the patient that s/he is going to conduct a cervical examination and confirm that the patient is ready to proceed. The trial coordinator will record the time of the first exam. The first provider will complete a cervical examination with a DilaCheck® device and sterile gloves using the techniques taught during training.

During or after the examination, before looking at the DilaCheck® device or his/her hand, the provider will verbally report his/her subjective cervical dilation measurement to the trial coordinator. Readings may be integers or fractional answers. The trial coordinator will record this number. The first provider will then look at the DilaCheck® device and read the measurement from the DilaCheck® measuring tape.

The trial coordinator will take a photograph from a secure camera of the DilaCheck® measurement. The trial coordinator may choose to take multiple photographs to ensure a clear image is captured. The coordinator and provider will use a neutral background to ensure no private health information (such as an image of the patient participant or hospital room) is included in the photograph. A white sheet of paper with the subject number will be provided to serve as a blank, secure background for the photograph(s).

The first provider will record two readings of the DilaCheck® measurement. The provider will write his/her measurements on the first Data Collection Form, fold the form, and hand it to the trial coordinator. The first will be his or her reading of the exact DilaCheck® measurement, which may be a fraction (any fraction). The second reading will be his or her reading of the DilaCheck® measurement rounded to the nearest integer; i.e. the second response can only be an integer, not a fraction.

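### The one-centimeter and two-or-more-centimeter bands leave most fractional disagreements ungraded, and make the one-centimeter test depend on how finely each arm is read

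*Combined protocol and SAP*

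**What the plan says.** The Statistical Analysis paragraph of the combined protocol and SAP first compares the proportion of pairs in which the two examiners differ at all. It then counts pairs whose "answers differed by one centimeter and by two or more centimeters for each group will be determined" and gives each of these two bands its own Student's t test. The paragraph ends: "These analyses will be completed for both the fractional and integral (non-fractional) sets of DilaCheck® measurement readings".

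The Data Collection paragraphs set the reading scales:

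- **Control Group:** one reading per examiner, with "Readings may be integers or fractional answers". No rounded control reading is collected.
- **Device Group:** two tape readings per examiner. One is exact, "which may be a fraction (any fraction"; the other is rounded by the examiner to a whole number.

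The plan does not say where a difference of 0.5 or 1.5 cm belongs, whether one centimeter means exactly 1 cm, or how finely the tape or the fingers are to be read.

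**The concern.** The two bands, together with exact agreement, cover every outcome only when both readings in a pair are whole numbers. With fractional readings, a pair 0.5, 0.75 or 1.5 cm apart counts as differing in the first analysis and then belongs to neither size band. A 1.5 cm disagreement goes ungraded while a smaller one of 1 cm is counted.

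An exact 1 cm difference also becomes rarer as the reading scale gets finer, whatever the examiner error. If the arms are read at different resolutions, the one-centimeter test compares resolutions as well as methods. The Protocol Summary presents the device's effect on the size of errors as a main finding of the simulator trial, so a spurious fall in 1 cm differences could be taken as confirmation in patients.

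**Working it through.** **The plan's own figure.** The plan gives no figure for either band. Its only sample-size figures concern overall agreement: 49% against 90%, SD 23, two-tailed 0.05. By the normal approximation, n = 2 × 23² × (1.960 + 0.842)² / 41² = 4.94. This rounds up to the stated five, taken as five per arm, and power at 25 per arm exceeds 99.9%. Nothing below changes this.

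**Inputs.** From the plan: 25 per arm, Student's t test, two-tailed 0.05. Assumed, because the plan does not give them:

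- independent normal examiner error with the same SD in both arms (0.5, 0.75 or 1.0 cm);
- true dilation uniform over the range;
- a reading grid for each arm.

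An SD of 0.5 cm gives 48.6% agreement on whole-centimeter readings, close to the projected control agreement of 49%. SDs of 0.75 and 1.0 cm give 35% and 27%, so 0.5 cm is the value that fits the plan best.

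**Step 1: where pairs fall (SD 0.5 cm, 1,000,000 simulated pairs, % of pairs).**

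| Reading grid | 0 | >0 to <1 | exactly 1 | >1 to <2 | 2 or more |
|---|---|---|---|---|---|
| 1 cm | 48.6 | 0 | 46.4 | 0 | 4.9 |
| 30% half-cm, rest whole | 37.0 | 21.4 | 34.1 | 4.0 | 3.5 |
| 0.5 cm | 27.0 | 43.1 | 21.5 | 6.8 | 1.5 |
| 0.25 cm | 13.9 | 64.2 | 10.5 | 10.5 | 0.8 |
| 0.1 cm | 5.6 | 76.4 | 4.2 | 13.2 | 0.6 |

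Hand check: the difference between two examiners has SD 0.5 × √2 = 0.707 cm, with density about 0.208 at 1 cm. For a fine grid g, the share at exactly ±1 cm is about 2 × g × 0.208. That is 10.4% at 0.25 cm and 4.2% at 0.1 cm, so the share is roughly proportional to g.

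On the 0.25 cm grid, (64.2 + 10.5) / (100 − 13.9) = 87% of all disagreements fall in neither band. At SD 1.0 cm the figure is 68%.

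**Step 2: the planned test on the fractional set, no true difference, device on a 0.25 cm grid.** Rejection rates come from exact binomial enumeration of the pooled t test.

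| Control readings | Rejection at SD 0.5 / 0.75 / 1.0 cm |
|---|---|
| All whole cm | 85 / 83 / 77% |
| 30% half-cm | 56 / 52 / 47% |
| All half-cm | about 19–20% throughout |

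With both arms on a half-centimeter grid, rejection is 5.5%, near nominal.

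Check of the first entry: the shares are 0.464 and 0.105. The average sample variance is (0.259 + 0.098) / 2 = 0.1785, so SE = √(0.1785 × 2/25) = 0.1195 and t = 0.359 / 0.1195 = 3.0, against a critical value of 2.01.

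**Step 3: reading one centimeter as 1 to <2 cm.** At SD 0.5 cm the shares become 46.4% (whole cm) and 21.0% (0.25 cm). Rejection with whole-centimeter controls is 50, 20 and 10% for the three SDs, and 6–10% with half-centimeter controls. The artefact shrinks but remains.

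**Step 4: the integer device set.** The device arm now shows 46.4% at exactly 1 cm, against 34.1% for controls with 30% half-centimeter readings. The artefact is reversed. With all half-centimeter controls, equal error makes the device look worse in 38–48% of trials.

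**Step 5: mean absolute difference.** If true dilation is uniform relative to the grid and both examiners use the same grid, rounding leaves the expected absolute difference unchanged at 2 × SD / √π. This is 0.56, 0.85 and 1.13 cm for the three SDs, and simulation gives the same values at every grid. For mixed whole- and half-centimeter controls it is 0.58, 0.86 and 1.14 cm. The t test on this quantity rejects about 5% of the time.

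**The case against.** A reader might infer that the device arm must show fewer one-centimeter errors by construction. The documents do not support that. They give neither the tape's graduation nor the fineness of control readings, and they allow fractions in both arms. The 77–85% figure needs every control reading to be a whole number and an assumed 0.25 cm device grid. On a common grid the artefact disappears.

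Three further points stand in part:

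- **Wording.** One centimeter is not defined and could mean 1 to <2 cm. That reading reduces the artefact, but it still leaves differences below 1 cm ungraded and has to be written down.
- **The parallel integer analysis.** The bands are exhaustive there for device readings, and any artefact runs against the device. The plan as a whole therefore does not favor the device. The integer set is not a clean check either, because no rounded control reading exists.
- **Fractional disagreements are not lost.** The any-difference analysis counts them, and a finer scale works against the device there. At SD 0.5 cm, fractional-set agreement would be 14% for the device against 49% for whole-centimeter controls, and that test would reject against the device 79% of the time. A spurious fall in 1 cm differences would appear beside visibly worse agreement.

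**Conclusion.** The concern holds as a defect in the secondary size-of-disagreement tests. Read literally, the bands have no place for differences of >0 to <1 or >1 to <2 cm, and the one-centimeter comparison depends on reading resolution, which the plan leaves open. The size of the false-positive risk is conditional: from nominal on a common grid, through about 19–20% and 47–56%, to 77–85% in the most unequal case examined. The direction depends on which device set is analyzed and on how often control examiners record fractions. These rates rest on the assumed SDs, grids and control reading habits. The ungraded gap itself rests only on the plan's wording. The primary any-difference outcome, the sample size and the power are not affected by this point. It should be corrected before analysis, but it does not threaten the trial's main comparison.

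**What to change.** - **Fractional set:** replace the two band tests with a between-arm comparison of the mean absolute difference between the two examiners, in cm. The planned Student's t test can be kept. Show the distribution in exhaustive bands (0; >0 to <1; 1 to <2; 2 or more cm) as description only, because exhaustive bands close the gap but still shift with resolution.
- **Integer set:** keep the one and two-or-more bands, but first round every control reading to the nearest whole number by a pre-specified rule that says what happens to halves. Both arms are then on one scale. Restricting the bands to pairs that happen to be whole numbers would not do: it would drop control patients with fractional readings after randomization, in one arm only.

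The cost is a few sentences in the Statistical Analysis paragraph and no new data. There are two small downsides. The fractional severity result becomes a mean in cm instead of two frequencies, and control readings are rounded by the analyst whereas device readings are rounded by the examiner.
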